8.3 Analyses Plans

8.3.1 Analysis Population

Patients with histopathology correlates will be analyzed for the primary aim. All remaining patients will be analyzed for the secondary endpoints.

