8.3.3 Central Data Analysis

Anonymized coded patient information (case report forms) will be captured in a central REDCap database hosted at the University of California at San Francisco (UCSF).

Anonymized and de-identified imaging data will be uploaded to a central website hosted at the Clinical Trials Network (CTN). PET data will be interpreted by three different readers in a random order at separate reading sessions. Cross sectional imaging (CT) obtained with the ⁶⁸Ga PSMA-11 PET will be available as anatomic correlate.

Central Read Interpretation: Final reads by the central read physicians for each subject will be interpreted as positive or negative for the presence of disease in the regions defined in section 8.2.1 (see table).

Reader Positivity and Negativity Definition: Regions of suspected disease will be graded on a two-point scale by each reader (0=Negative or 1=Positive). A region will be judged as positive if at least one lesion in this region is visually positive. Criteria for visual interpretation is described in section 8.3.3.

Reader Training: ⁶⁸Ga PSMA-11 PET/CT reading training set and guides will be provided and completion of this training will be required for all central review readers.

Case report forms will be provided to the FDA for review, when requested.

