8.3.4 Analysis of Primary Endpoints

Primary endpoint: PPV on a per-patient basis of ⁶⁸Ga-PSMA-11 PET for detection of prostate cancer confirmed by histopathology will be calculated and reported along with the corresponding two-sided 95% confidence intervals. The confidence intervals will be constructed using the Wilson score method.

a) Imaging interpretation ⁶⁸Ga-PSMA-11 PET:

PET images will initially be interpreted by a board certified nuclear medicine physician or a board certified radiologist experienced in reading PET at the time of the imaging study at the University of Michigan. These interpretations will not be used for final evaluation. Upon request, anonymized ⁶⁸Ga-PSMA PET/CT imaging data are sent to the FDA for further review.

Visual interpretation:

Regions of suspected disease will be graded on a two-point scale by each reader (0=Negative or 1= Positive). A region will be judged as positive if at least one lesion in this region is visually positive.

- i) Lymph nodes will be considered positive if the ⁶⁸Ga-PSMA-11 uptake is focal and greater than blood pool (adjacent or mediastinal blood pool). Pelvic lymph nodes will be subclassified according to their localization as follows: R/L obturator, R/L external iliac, R/L internal iliac and other (total of 7 subgroups).
- ii) Visceral lesions will be considered positive if the ⁶⁸Ga-PSMA-11 uptake is focal and greater than physiologic background activity of the involvement organ or anatomic site.

- iii) Bone lesions will be considered positive if the ^{68}Ga -PSMA-11 uptake is focal and greater than physiologic bone marrow.
- iv) Prostate bed and prostate lesions will be considered positive if the ^{68}Ga -PSMA-11 uptake is focal and greater than physiologic background activity of the involvement organ or anatomic site.

b) Follow-up Imaging:

All patients are expected to be followed up as part of clinical care within 3-12 months with conventional imaging (dedicated CT, MRI and/or bone scan). Interpretation of follow-up imaging will be performed by local read. The follow-up conventional imaging should be the same modality/modalities as the initial staging work-up to allow reproducible and accurate comparisons.

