^{68}Ga -PSMA-11 PET positive findings will be validated as true or false positive as outlined in more detail below. False negative ^{68}Ga -PSMA-11 PET findings may be determined based on biopsies obtained from lesion identified on conventional imaging that are negative on ^{68}Ga -PSMA-11.

Rationale for applied response criteria:

RECIST 1.1 defines a size decrease of at least 30% as response (either partial or complete), while an increase of at least 20% is considered progressive disease ^{42,43}. The decline of serum PSA of 50% or more is a commonly used criterion for treatment response following systemic treatment of metastatic prostate cancer ⁴⁴⁻⁴⁶.

Following the ^{68}Ga -PSMA-11 PET/CT scan, focal therapies of metastatic lesions may be performed without systemic treatment. Therefore, anatomic size variations can be suitable endpoints in absence of histological verification. In patients with solitary lesions, PSA reductions following focal treatment may indicate a true positive scan finding even in absence of significant size changes.

^{68}Ga -PSMA-11 PET validation based on follow-up imaging:

- i) Lymph nodes will be assessed by change in size. ^{68}Ga -PSMA-11 positive lymph nodes will be considered:
 - (1) True positive:
 - If on follow-up imaging within 3-12 months, lymph nodes seen on CT or MRI decrease by more than 30% (for patients undergoing systemic treatment of focal therapy at this site) or increase by more than 20% in short axis diameter (with a minimum of 3 mm in change in size).
 - If patients with solitary lymph node regions show a decrease of PSA by greater than 50% after targeted treatment (i.e. external beam radiation) and the lymph nodes do not change in size (less than 30% decrease or less than 20% increase in short axis diameter).
 - (2) False positive:

- If on follow-up imaging within 3-12 months, sites of initial ⁶⁸Ga-PSMA-11 positive lymph node lesions seen on CT or MRI decrease by more than 30% *without* systemic therapy or focal therapy at this site.

- If ⁶⁸Ga-PSMA-11 positive lymph node lesions do not meet the criteria for above false positive or true positive findings.

ii) Visceral lesions (non-lymph node soft tissue or organ) will be assessed by change in size. ⁶⁸Ga-PSMA-11 positive visceral lesions will be considered:

(1) True positive:

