- If on follow-up imaging within 3-12 months, visceral lesions seen on CT or MRI decrease by 30% (for patients undergoing systemic treatment of focal therapy at this site) or increase by 20% in largest diameter.

- If patients with solitary visceral metastasis show a decrease of PSA by greater than 50% after targeted treatment (i.e. external beam radiation) and lesions do not change in size (less than 30% decrease or 20% increase in largest diameter).

(2) False positive:

- If on follow-up imaging within 3-12 months, sites of initial ⁶⁸Ga-PSMA-11 positive lymph node lesions seen on CT or MRI decrease by more than 30% *without* systemic therapy or focal therapy at this site.

- If ⁶⁸Ga-PSMA-11 positive lymph node lesions do not meet the criteria for above false positive or true positive findings.

iii) ⁶⁸Ga-PSMA-11 positive bone lesions will be considered:

(1) True positive:

- If there was a corresponding positive sclerotic lesion on the CT portion of the ⁶⁸Ga-PSMA-11 PET.

- If there is focal uptake seen on the baseline bone scan performed within one month of ⁶⁸Ga-PSMA-11 PET.

- If there is a lesion noted on the initial MRI performed within one month of ⁶⁸Ga-PSMA-11 PET.

- If within 12 months follow-up CT demonstrates development of sclerosis.

- If within 12 months follow-up MRI demonstrates a new bone lesion.

- If within 12 months follow-up bone scan demonstrates new focal uptake.

(2) False positive:

- If ⁶⁸Ga-PSMA-11 positive bone lesions do not meet the criteria for true positive findings.

iv) ⁶⁸Ga-PSMA-11 positive prostate bed and prostate lesions will be considered:

(1) True positive:

- If on follow-up imaging within 12 months, lesions seen on CT or MRI decrease by 30% (for patients undergoing systemic treatment of focal therapy at this site) or increase by 20% in largest diameter.
- If patients with prostate bed lesions show a decrease of PSA by greater than 50% after targeted treatment (i.e. external beam radiation) and lesions do not change in size (less than 30% decrease or 20% increase in largest diameter).

(2) False positive:

- If on follow-up imaging within 3-12 months, sites of initial ⁶⁸Ga-PSMA-11 positive lymph node lesions seen on CT or MRI decrease by more than 30% *without* systemic therapy or focal therapy at this site.
- If ⁶⁸Ga-PSMA-11 positive lymph node lesions do not meet the criteria for above false positive or true positive findings.

c) Histopathology/Biopsy:

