8.3.5 Central Analysis of Secondary Endpoints

1. PPVs on a per-patient and per-region-basis of ⁶⁸Ga-PSMA-11 PET for detection of tumor location confirmed by histopathology/biopsy and conventional imaging follow-up will be calculated and reported along with the corresponding two-sided 95% confidence intervals. The confidence intervals will be constructed using the Wilson score method.
2. Sensitivity on a per-patient and per-region basis of ⁶⁸Ga-PSMA-11 PET for detection of tumor location confirmed by histopathology/biopsy will be summarized in tabular format. Ninety-five percent confidence intervals of sensitivity and PPV will be calculated using the Wilson score method.
3. Detection rates on a per-patient basis of ⁶⁸Ga-PSMA-11 PET stratified by PSA value (0.2 - <0.5, 0.5 - <1.0, 1.0 - <2.0, 2.0 - <5.0, 5.0) will be summarized in tabular format and compared between PSA strata using chi-square analysis.
4. The impact of ⁶⁸Ga-PSMA-11 PET on clinical management in BCR patients will be evaluated using surveys of the treating physician or practitioner before, at 1 (2-30 days) and 6 (range 3 - 12) months after the ⁶⁸Ga-PSMA-11 PET scan (see data collection sheet, section 44 eResearch). The results will be analyzed and provided in coded form for central analysis.
5. Safety will be reported descriptively as rates of patient reported adverse events.

9 Study Management

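### Same-scan CT alone can confirm a bone lesion, so the secondary PPV's reference is not independent of the PET/CT; separately, the prostate-bed true and false positive rules do not match

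*Combined protocol and SAP*

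**What the plan says.** The validation rules are in section 8.3.4(b), under the primary endpoint heading.

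- **Bone.** Any one of six findings makes a PET-positive lesion a true positive. The first is "If there was a corresponding positive sclerotic lesion on the CT portion of the" index PET. The others are a bone scan or an MRI within one month of the PET, or new findings on CT, MRI or bone scan within 12 months. A lesion that meets none of these is a false positive.
- **Prostate bed.** With treatment, a lesion is a true positive "If on follow-up imaging within 12 months, lesions seen on CT or MRI decrease by 30" per cent; growth of 20% also counts. The false positive rule for shrinkage without therapy begins "If on follow-up imaging within 3-12 months, sites of initial" and goes on to speak of lymph node lesions. So does the residual rule beneath it.
- **Lymph nodes.** The true positive rule reads "If on follow-up imaging within 3-12 months, lymph nodes seen on CT or MRI decrease by more than 30" per cent (with treatment), and the false positive window is the same. Visceral lesions also have 3-12 months on both sides.

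On follow-up generally, the same section says that all patients are "expected to be followed up as part of clinical care within 3-12 months with conventional imaging".

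Section 8.3.3 makes the CT available to the central readers: "Cross sectional imaging (CT) obtained with the" PET serves as their anatomic guide.

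The two PPVs have different references. For the primary, section 8.3.1 says: "Patients with histopathology correlates will be analyzed for the primary aim". Item 1 of section 8.3.5 defines the secondary PPV, per patient and per region, as that of "PET for detection of tumor location confirmed by histopathology/biopsy and conventional imaging follow-up".

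**The concern.** A PPV is informative when the reference that confirms a positive call is separate from the test that made it. The objectives name the test as PET/CT. If the CT half is in front of the reader and can then confirm the call by itself, part of the index test acts as its own reference. A bone focus with benign sclerosis could be read as positive and then confirmed without further evidence, and no later imaging could reverse it, because the bone false positive rule is only a residual.

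In the prostate bed, a scan before 3 months can confirm a lesion but cannot count against it under the specific shrinkage rule. Section 5.3 collects all conventional imaging over the 12 months after the scan, so such scans may be in the data.

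At stake is the credibility of the secondary composite PPV, which is to be pooled across sites for a future NDA.

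**Working it through.** The plan gives no PPV or bias figure that rests on these rules, so there is none to reproduce. The 80% power in section 8.2.1 belongs to the histopathology PPV and does not depend on them.

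**1. The rules side by side (8.3.4(b))**

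| Region | True positive imaging | False positive shrinkage rule | Residual rule is worded for |
|---|---|---|---|
| Lymph nodes | 3-12 months | 3-12 months | lymph nodes |
| Visceral | 3-12 months | 3-12 months | lymph nodes |
| Bone | baseline evidence, or follow-up within 12 months | none | bone lesions |
| Prostate bed | within 12 months | 3-12 months | lymph nodes |

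Only the prostate bed has two stated windows that differ. The visceral and prostate-bed false positive rules name the wrong region. Read literally, those two regions have no false positive rule of their own.

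**2. Direction of the same-scan CT criterion**

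Let T be the units (bone-region patients, or patients) that are true positive on other evidence, C those that are true positive only through the same-scan CT, and F the false positives.

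- Planned PPV: (T + C)/(T + C + F)
- CT-only set aside: T/(T + F). Planned minus this = C·F/[(T + F)(T + C + F)], which is never negative.
- CT-only counted as unconfirmed: T/(T + C + F). Planned minus this = C/(T + C + F), which is never negative.

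Relative to a rule without it, the criterion can therefore only raise the PPV or leave it unchanged.

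**3. Illustration (all counts assumed)**

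Forty PET-positive bone patients, 30 true positive, F = 10; planned PPV 30/40 = 75%.

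| C | Set aside | Counted as unconfirmed |
|---|---|---|
| 3 | 27/37 = 73.0% | 27/40 = 67.5% |
| 10 | 20/30 = 66.7% | 20/40 = 50.0% |

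**4. Net bias of the whole bone rule set**

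Let t be the true bone PPV, f the share of non-cancer foci wrongly confirmed by baseline evidence, and g the share of true lesions that lack confirming evidence and so count as false positive.

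- Observed PPV = t(1 − g) + (1 − t)f
- Observed minus true = (1 − t)f − t·g

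The documents give none of the three for bone. Taking t = 0.75, the plan's hypothesised per-patient PPV:

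- g = 0 and f = 0.1, 0.3, 0.5: +2.5, +7.5, +12.5 points
- f = 0 and g = 0.1, 0.2, 0.3: −7.5, −15.0, −22.5 points
- the two cancel when f = t·g/(1 − t) = 3g; at t = 0.50 they cancel when f = g

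The sign depends on f and g, which are unknown.

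**5. Reach into the primary PPV**

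Section 8.3.4(c) sends indeterminate bone pathology to follow-up imaging under the rules above. Section 8.2.1 expects about 24 biopsied patients and a bone share of 35% of biopsied disease: 0.35 × 24 = 8.4. Only the indeterminate ones among these could be affected. One reclassified patient would move the primary PPV by 1/24 = 4.2 points.

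**The case against.** The best defence is that bone positivity is defined by uptake alone, relative to marrow. CT is an aid to location and not a criterion, so sclerosis is a separate physical finding. This stands in part: the CT is not the positivity rule. But the readers see it, and it is neither a follow-up scan nor a dedicated one, so independence is incomplete.

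A second defence is that follow-up is left to standard care, and that without the CT criterion true bone metastases lacking other imaging would be counted as false positives. This stands. It is why removing the criterion from the main analysis would exchange one bias for another.

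A third is that the prostate-bed mismatch matters little: follow-up is expected at 3-12 months, and untreated shrinkage never meets the true positive rule. If the residual rule is meant to cover the prostate bed, early untreated shrinkage falls to false positive anyway. This stands on that reading, but the residual rule as written covers only lymph nodes.

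A reader might also infer that the plan's PPV is biased upward overall, or that every region has its own mismatched windows. The documents support neither. The residual rules push the other way by an unknown amount, node and visceral windows agree, and bone has no false positive window to compare.

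**Conclusion.** The point holds in a limited form. The same-scan CT criterion makes index test and reference partly dependent for bone lesions, and it can only raise or leave unchanged the secondary composite PPV, for the bone region and per patient, relative to a rule without it. Its size cannot be computed from the documents; the falls of 2 to 25 points in the illustration follow from assumed counts. The 35% bone share describes biopsied disease and should not be used to weight imaging-validated lesions.

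The prostate-bed rules contain a real mismatch of windows, and the visceral and prostate-bed false positive rules carry lymph node wording. Both are drafting defects to reconcile.

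Because the rules sit in the primary endpoint section, a reader might infer that the primary result is at risk. It is confirmed by histopathology in patients who have it. The CT criterion could enter only through indeterminate bone biopsies, and it is not clear that the referral to follow-up imaging there includes this baseline criterion.

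**What to change.** 1. Keep the planned analysis. Add to section 8.3.5 a report of the secondary bone and per-patient PPV, with Wilson intervals, in which lesions confirmed only by the same-scan CT (no bone scan, MRI, follow-up imaging or histology) are (a) set aside and (b) counted as unconfirmed.
2. In section 8.3.4(b)(iv), use the 3-12 month window that 8.3.4(b) states for follow-up in both prostate-bed imaging rules.
3. Reword the visceral and prostate-bed false positive rules, including the residual ones, so that each names its own region.

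The cost is one sensitivity table and some wording. The data record must show which criterion confirmed each bone lesion. Where CT-only confirmations occur, expect the sensitivity bone PPV to be lower, and less precise when they are set aside, by an amount the documents do not allow to be computed. Prostate-bed lesions whose only confirming scan falls before 3 months would lose that confirmation.

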at the time of scanning, PSA doubling time, PSA velocity, initial Gleason score, ongoing androgen deprivation therapy, patient age and amount of injected tracer activity in cohorts of 319, 248 and 1007 patients with BCR^{25,27,29}. All studies suggested that the absolute PSA level and androgen deprivation therapy were associated with a positive ⁶⁸Ga-PSMA scan, while the PSA doubling time and Gleason score at initial presentation were not a significant predictors of scan positivity.

Improvements in the detection of recurrent prostate cancer have profound effects on patient management²⁸. In a recently published Australian multi-center trial including 323 patients with biochemical evidence of recurrent disease and equivocal conventional imaging, ⁶⁸Ga-PSMA PET/CT changed the management of prostate cancer in 62% of cases. In this study, a substantial impact was documented with a significant reduction in the number of men in whom the site of disease recurrence was unknown and significant increases in the detection of presumed oligometastatic and polymetastatic disease. Compared to standard of care diagnostics (including imaging), additional sites of disease were detection in 32% as local recurrence, 43% as nodal disease and 20% as metastatic (mostly to bone)³². ⁶⁸Ga-PSMA has a significantly higher sensitivity and specificity than 99mTc-bone scanning in 126 patients with prostate cancer, of whom 75 were found to present with osseous metastatic disease³³.

Overtreatment and undertreatment of BCR occurs³⁴. Due to the lack of accurate imaging, salvage RT of prostate bed without identification of the disease location is commonly performed. The lack of targeted focal treatment of metastatic disease may limit the success of such treatment. Also, ⁶⁸Ga-PSMA identifies a high detection rate of prostate cancer recurrence outside of the prostatic fossa³⁵. This clearly indicates the need for prospective trials to evaluate the changes in RT volumes or disease management and their outcomes.

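### The PSA-fall rule can confirm a prostate-bed lesion that is not the only lesion, and no PSA rule addresses concurrent systemic therapy, so a false-positive region can count as true positive in the secondary PPV

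*Combined protocol and SAP*

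**What the plan says.** Section 8.3.4 b) classifies PET-positive lesions by follow-up when there is no biopsy. Three lesion classes have a PSA rule. Each needs a targeted treatment, a PSA fall of more than 50% and no qualifying change in size.

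- Lymph nodes, i): "If patients with solitary lymph node regions show a decrease of PSA by greater than 50% after targeted treatment".
- Visceral lesions, ii): "If patients with solitary visceral metastasis show a decrease of PSA by greater than 50% after targeted treatment".
- Prostate bed and prostate, iv): "If patients with prostate bed lesions show a decrease of PSA by greater than 50% after targeted treatment (i.e. external beam radiation").

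Bone lesions, iii), have no PSA rule.

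The rationale ahead of these rules says "In patients with solitary lesions, PSA reductions following focal treatment may indicate a true positive scan finding", even without a size change. It introduces the 50% threshold as a "commonly used criterion for treatment response following systemic treatment of metastatic prostate cancer". It also remarks that "focal therapies of metastatic lesions may be performed without systemic treatment".

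Section 5.4 leaves concomitant care open, Section 6.2 prohibits no medication, and Section 3.2.2 excludes only current investigational therapy for prostate cancer.

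The rules feed the secondary PPV, per patient and per region (Sections 2.2, 2.3.2 and 8.3.5). It is analysed centrally in the pooled 1,500 patients. Region 1 in Table 1 is the prostate bed.

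**The concern.** Every enrolled man has a rising PSA, so he is likely to have disease somewhere. A PSA fall shows that treatment reached disease. It shows that a particular PET-positive region held disease only if nothing else that was treated could explain the fall. The word solitary supplies part of that condition, and the bed rule lacks it. The other part, absence of concurrent systemic therapy, appears in none of the three rules.

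The objective is PPV for tumor location. When these conditions fail, the rule records response to therapy rather than correctness of the PET call. Little histology is available to correct this: Section 8.2.1 reports biopsies of PET-positive lesions in 13 of 316 evaluable subjects (13/316 = 4.1%). Most composite classifications will therefore come from the follow-up rules. The pooled data are intended to support an NDA.

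**Working it through.** **1. The texts side by side**

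| Source in 8.3.4 b) | Limited to solitary disease? | Concurrent systemic therapy addressed? |
|---|---|---|
| Rationale for PSA evidence | Yes, solitary lesions | No |
| Nodes, i) | Yes, solitary nodal regions | No |
| Visceral, ii) | Yes, solitary metastasis | No |
| Prostate bed, iv) | No | No |

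The size rules in the same section do separate shrinkage with treatment from shrinkage without it. The PSA rules make no comparable distinction, although the rationale ties the 50% threshold to systemic response.

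**2. Which PPV is affected**

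- *Bed focus false, nodes real, both irradiated.* The nodes explain the PSA fall, yet the bed is scored true positive. Region-1 PPV is too high. Per-patient PPV is unaffected, because the patient does have PET-detected cancer.
- *Only PET focus false, targeted treatment given together with systemic therapy.* The fall may come from disease that PET did not show. Region and patient are both scored true positive. This can happen under all three PSA rules.
- *Bed the only PET-positive region, bed radiation, no systemic therapy.* The fall is reasonable evidence of disease in region 1. There is no objection here.
- *Primary PPV.* It is confirmed by histopathology in patients with histopathology correlates (Sections 8.3.1 and 8.3.4). The rerouting of negative biopsies to follow-up in 8.3.4 c) covers nodes and bone, not the bed.

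**3. Size: illustration only**

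The documents give no stated figure to reproduce. They do not say how many lesions PSA would classify, or how many men receive concurrent systemic therapy. Let p be the true region-1 PPV and q the share of false-positive bed calls relabelled by the PSA rule. If every real lesion is confirmed:

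apparent PPV = p + (1 − p) × q, with q assumed to be 10% to 50%.

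- p = 50%: 0.50 + 0.50 × 0.10 = 55%; 0.50 + 0.50 × 0.50 = 75%.
- p = 75%: 0.75 + 0.25 × 0.10 = 77.5%; 0.75 + 0.25 × 0.50 = 87.5%.

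For all lesions together, suppose only bed lesions are affected, PPV is equal across regions, and the bed holds 30% of lesions. Section 8.2.1 gives 30% for biopsied disease, so using it here is an assumption. Then apparent PPV = p + 0.30 × (1 − p) × q:

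- p = 50%: 51.5% to 57.5%.
- p = 75%: 75.75% to 78.75%.

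**4. The opposite pull**

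Real lesions can also fail confirmation. If a share c of real bed lesions is confirmed and the rest count as false positive, then apparent PPV = c × p + (1 − p) × q. Assume p = 0.70 and q = 0.5 × 0.9 = 0.45 (half of the false-positive calls treated in a confounded way, 90% of those with a qualifying PSA fall):

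- c = 1: 0.70 + 0.30 × 0.45 = 0.835.
- c = 0.75: 0.525 + 0.135 = 0.660, below the true 0.70.
- Break-even: c = (0.70 − 0.135)/0.70 = 0.81.

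The PSA rule itself moves lesions only into the true-positive class. The sign of the net error depends on the other rules.

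**The case against.** Several counter-arguments have force.

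- **The bed is already one region.** That may be why the word solitary is missing. The nodal rule speaks of solitary nodal regions and does not clearly exclude a simultaneous bed lesion either. This weakens the contrast with nodes but not with the rationale, which speaks of solitary lesions. Being one region does not make the bed the only PET-positive region.
- **Systemic therapy alone never triggers the rule.** This is correct: targeted treatment, a PSA fall and stable size are all required. The gap concerns systemic therapy given alongside targeted treatment.
- **Other defaults work against PET.** Nodal and bone lesions that meet no true-positive criterion count as false positive. Under the visceral and bed headings the printed default names lymph node lesions, so its reach there is unclear. This stands, and it is why no net direction is claimed for the overall composite.

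A reader might also infer more than the documents support:

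- **That the rationale already requires absence of systemic therapy.** It does not. The remark that focal therapy may be given without systemic treatment is descriptive and leads into the size criteria. The silence on systemic therapy is a gap, not a breach of a stated rule.
- **That any PSA fall after bed radiation is uninformative**, because Section 1.2 says "salvage RT of prostate bed without identification of the disease location is commonly performed". At the resolution of the endpoint, a fall after bed-only radiation without systemic therapy supports disease in region 1, even if the exact focus was wrong.

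**Conclusion.** The bed rule is wider than its own rationale, and all three PSA rules leave concurrent systemic therapy unaddressed. Nothing elsewhere in the documents closes either gap. As written, the plan can score a false-positive bed region as true positive. The rule biases the secondary region-1 PPV upward. Where systemic therapy is concurrent, it can also raise the nodal, visceral and per-patient composite PPV. The primary PPV does not rest on it.

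The size cannot be computed from the documents. The region-1 illustration, 2.5 to 25 points, rests wholly on the assumed q and on every real lesion being confirmed. It should not be read as an estimate, nor carried over to the overall composite: under the further assumptions above, the same q gives about 0.8 to 7.5 points there, before any opposite pull. A claim that the overall composite PPV is necessarily inflated would go too far.

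**What to change.** These changes concern the reference standard and its reporting, not patient care.

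1. In 8.3.4 b) iv), let a PSA fall confirm a bed lesion only when the bed is the only PET-positive region, in line with the stated rationale.
2. In the PSA rules of i), ii) and iv), state that a fall under concurrent systemic therapy does not by itself confirm a lesion.
3. In 8.3.5, report composite per-region and per-patient PPV with and without PSA-only confirmations, overall and by concurrent systemic therapy. State how the lesions that lose confirmation are counted in the denominator. Dropping them as not evaluable would change the denominator and sit badly with the false-positive defaults, so that choice must be explicit.

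Cost: wording and one extra tabulation. Follow-up by chart review (Section 3.3.2) and review of clinical notes (Section 5.3) are already planned. The documents do not show whether PSA values and systemic therapy dates reach the central database. Some lesions will lose confirmation, and PPV may be less favourable. The wording must also match the other sites, because endpoints were aligned for pooling and 316 subjects were already evaluable at this version. If the pooled definitions cannot change mid-study, item 3 alone suffices.
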